11.1 Analysis sets

For all analysis sets, subjects will be analyzed according to the study treatment(s) received.

The safety analysis set will include all subjects that received any study drug.

The PK analysis set will include all subjects with at least one available valid (i.e. not flagged for exclusion) PK concentration measurement, who received any study drug and with no protocol deviations that impact on PK data.

The PD analysis set will include all subjects with available PD data and no protocol deviations with relevant impact on PD data.

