Each patient will come to the study site for the follow-up evaluations on Day 169, Day 197, Day 225, Day 253, Day 281, Day 309, and Day 337, respectively. Patients should remain on their standard of care therapies. Dose of standard of care (SoC) therapies (see eligibility criteria and permitted co-medications) must remain unchanged during the study. However, in case of SoC related toxicities, doses of concomitant medications may be adjusted at the investigator's discretion. For patients who are taking corticosteroids at baseline, a predefined steroid regimen (Table 1-1) will be implemented including a taper for patients who receive more than 10 mg per day at baseline. After Week 17 (Visit 106), patients should not receive a steroid dose higher than 10 mg per day (prednisone equivalent).

Safety assessments will include physical examinations, ECGs, vital signs, standard clinical laboratory evaluations (also including serum amylase and lipase), hematology (including blood coagulation assays), blood chemistry, urinalysis, adverse event, serious adverse event and AEs of special interest.

[figure not shown]
Proteinuria will be assessed using urine samples collected in the patients' home (first morning void sample) and at clinic (clinic spot urine sample)

PK/PD and immunogenicity assessments at pre-dose, and during treatment and follow up periods include (i) free CFZ533 in plasma (C_{trough} or C_{min}, and C_{max} in steady state conditions), total soluble CD40 in plasma, and (iii) anti-CFZ533 antibodies in plasma.

Commercially Confidential Information

Table 1-1 Predefined steroid tapering scheme

Dose (x) at BL (prednisone equivalent) [mg/day]	Visit 103 (Day 29±2)	Visit 104 (Day 57±2)	Visit 105 (Day 85±2)	Visit 106 (Day 113±2)	Visit 199 (Day 141±2)	After Visit 201 (Day 169±3)
0<x≤10	Maintain the baseline dose			Half the baseline dose	10	As needed
10<x≤20	Maintain the baseline dose			10	10	As needed
20<x≤30	Maintain the baseline dose		20	10	10	As needed

Figure 1-1 Study design

* CFZ533 or placebo 10 mg/kg i.v. on Day 1, 15, 29, 57, 85, 113, and 141

2 First interpretable results (FIR)

Commercially Confidential Information

3 Interim analyses

Commercially Confidential Information

4 Statistical methods: Analysis sets

For subjects for which the actual treatment received does not match the randomized treatment the treatment actually received will be used for the analysis.

The safety analysis set will include all subjects that received any study drug.

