The PK analysis set will include all subjects with available PK data and no protocol deviations with relevant impact on PK data.

The PD analysis set will include all subjects with available PD data, and experienced no protocol deviations with relevant impact on PD data.

Selected summaries with and without the data obtained after treatment discontinuation may also be presented.

The analysis sets and protocol deviation codes are related as follows:

Table 4-1 Protocol deviation codes and analysis sets

Category Deviation code	Text description of deviation	Data exclusion
Subjects are excluded from PK analysis in case of these PDs:		
INCL01	Understand the study procedures and provide written informed consent before any study related assessment is performed.	Exclude subject from PK analysis set
INCL04	Histological diagnosis of proliferative lupus nephritis World Health Organization (WHO) ISN/RPS (Weening et al 2004) Class III or IV within 5 years of screening.	Exclude subject from PK analysis set
INCL06	First morning void or spot urine UPCR ≥ 0.5 mg/mg (56.52 mg/mmol) at Screening visit and Baseline visit	Exclude subject from PK analysis set
Subjects are excluded from PD analysis in case of these PDs:		
INCL01	Understand the study procedures and provide written informed consent before any study related assessment is performed.	Exclude subject from PD analysis set
INCL04	Histological diagnosis of proliferative lupus nephritis World Health Organization (WHO) ISN/RPS (Weening et al 2004) Class III or IV within 5 years of screening.	Exclude subject from PD analysis set
INCL06	First morning void or spot urine UPCR ≥ 0.5 mg/mg (56.52 mg/mmol) at Screening visit and Baseline visit	Exclude subject from PD analysis set
Subjects are excluded from PK and PD analysis in case of these PDs:		
INCL01	Understand the study procedures and provide written informed consent before any study related assessment is performed.	Exclude subject from PK and PD analysis sets
INCL04	Histological diagnosis of proliferative lupus nephritis World Health Organization (WHO) ISN/RPS (Weening et al 2004) Class III or IV within 5 years of screening.	Exclude subject from PK and PD analysis sets
INCL06	First morning void or spot urine UPCR ≥ 0.5 mg/mg (56.52 mg/mmol) at Screening visit and Baseline visit	Exclude subject from PK and PD analysis sets

If updates to this table are needed, an amendment to the SAP needs to be implemented prior to DBL.

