5.3 Pharmacokinetic/pharmacodynamics interactions

PK/PD analysis (e.g. incl. free CFZ533 and total soluble CD40 in plasma) may be explored graphically. Modeling of PK/PD data using a population approach may be performed as appropriate and will be reported if necessary in a separate, standalone modeling and simulation report.

6 Statistical methods for Pharmacodynamic (PD) parameters

Baseline is defined as the last available value prior to dosing and will include Screening if no other value after Screening is available.

For UPCR and UACR where the analyses are split between first morning void and clinic spot samples then the last available value prior to dosing from the first morning void or clinic spot sample respectively will be used. For the analyses that use the first morning void when available and the clinic spot sample if it is not available then the last available first morning void prior to dosing will be used as the baseline, if there are no first morning void values available prior to dosing then the last available clinic spot sample prior to dosing will be used as the baseline for these analyses.

Summary of key estimands for efficacy

Estimands are defined for this trial to address the efficacy objectives of the trial and to provide supportive evidence for those objectives. These estimands are defined in detail in the subsequent sections and are summarized in Table 6-1. The analysis for other safety/efficacy/PK data are described in other sections of this SAP.

Table 6-1 Summary of key estimands

	Estimand	Variable estimand is based on	Section
P1	Primary 1 – renal proteinuria	Ratio from baseline in urinary protein creatinine ratio (UPCR) at Week 25	6.1
S2	Secondary 1 - renal	Proportion with complete renal remission (CRR)	6.2

6.1 Primary estimand 1

The primary estimand 1 addresses the second primary objective:

- To assess the effect of CFZ533 on renal proteinuria in moderately active lupus nephritis patients after 24 weeks of treatment as an add-on therapy to standard of care as compared to placebo.

This estimand addresses the scientific question of whether treatment with CFZ533 reduces UPCR in moderately active lupus nephritis patients after 24 weeks of treatment without death, rescue medication and treatment discontinuation as an add-on therapy to standard of care.

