6.1.1 Definition of primary estimand 1: UPCR

- Population: moderately active proliferative lupus nephritis patients.
- Variable: Ratio from baseline in UPCR at Week 25
- Treatment: CFZ+SOC, Placebo+SOC
- Summary Measure: Ratio of Geometric Means of CFZ533 versus placebo.

Hypothetical strategy will be used to deal with death, rescue medication and treatment discontinuation inter-current events. Data from patients taking rescue medication during the trial (or failing to tolerate steroid taper, for patients receiving oral corticosteroid at baseline) will be excluded from the date of rescue medication intake or failure of the steroid taper. Data from patients who discontinue study treatment will also be excluded, from the date of study drug discontinuation. A medical assessment prior to database lock will determine which patients are deemed to have failed the steroid taper based on clinical relevance of the steroid dose taken and the potential impact on the primary endpoint.

No other inter-current events will be taken into account in the estimand.

Commercially Confidential Information

Statistical analysis model

The ratio from baseline in UPCR will be log transformed prior to the analysis. A repeated measures model will be fitted with factors for treatment group (CFZ533 or placebo) and visit (e.g. Week 5, 9, 13 etc.). The model will also include a factor for the prednisone dose-equivalent at baseline (≤ 10 mg, > 10 mg) based on the concomitant medication information in the database rather than the stratification factor from the randomization. Log-transformed baseline UPCR will be included in the model as a covariate along with the interactions between visit and all of the fixed effects and the log-transformed baseline by visit interaction. A normal errors model will be assumed with an unstructured covariance matrix to account for the correlation within subjects. The model will be estimated using maximum likelihood techniques. If there are values of 0 then 0.1 will be added to all the UPCR data prior to the log transformation.

At each of the visits, the difference between the CFZ533 and placebo group will be estimated (along with its corresponding 95% confidence interval) and then back-transformed to provide an estimate of the ratio between treatment groups.

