Sensitivity analyses will be considered if a substantial proportion of patients (i.e. more than 15%) receive rescue medicine or discontinue from study treatment. Multiple imputation models may be used to assess the robustness of the missing at random assumption of the primary analysis.

In addition if more than 15% of patients fail to tolerate the steroid taper scheme, a supportive analysis of efficacy using time to lack of taper as endpoint will be conducted. Additional analyses including all patients regardless of their adherence to treatment will be performed.

The adequacy of the model will be assessed by inspecting residual plots.

Data will be listed by treatment and timepoint. Descriptive summary statistics will include mean (arithmetic and geometric), SD, and CV (arithmetic and geometric), median, minimum and maximum and will be presented by treatment and timepoint. Outputs will be provided for the raw UPCR values and also the ratio from baseline. An additional summary will also be provided by baseline steroid dose and also for subjects with biopsies within 2 years prior to randomization and 5 years prior to randomization separately.

Geometric mean (95% CI) of ratio from baseline profiles will be presented along with geometric mean ratio to placebo profiles. These figures will use the data obtained from the above model. Additional profiles of geometric mean (SE) UPCR data will be presented based on the raw data. For these plots the data will be log transformed and the mean and standard error calculated, the standard error will be added/subtracted from the mean on the log scale and then back transformed to obtain the error bars for the plot.

The above outputs will also cover the outputs needed for the secondary objective to assess UPCR at different timepoints.

The above analyses will also be repeated using only the data from the first morning void and clinic spot sample separately.

6.2 Secondary estimand 1

The secondary estimand 1 addresses the secondary objective:

- To assess the effect of CFZ533 on relevant renal outcomes at different time points.

This estimand addresses the scientific question of whether treatment with CFZ533 has a beneficial effect on renal outcomes at different timepoints without death, rescue medication and treatment discontinuation as an add-on therapy to standard of care.

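### The primary UPCR comparison is grouped by treatment received, and no efficacy set grouped by randomised arm is defined or named

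*Protocol*

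**What the plan says.** Protocol 11.1 sets one grouping rule for everything: "For all analysis sets, subjects will be analyzed according to the study treatment(s) received". SAP section 4 (Statistical methods: Analysis sets) applies it to mismatches: "For subjects for which the actual treatment received does not match the randomized treatment the treatment actually received will be used for the analysis". Neither sentence exempts efficacy.

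Both documents define three sets only: safety, PK and PD. Protocol 11.1 defines the last of these as follows: "The PD analysis set will include all subjects with available PD data and no protocol deviations with relevant impact on PD data". SAP Table 4-1 then lists deviation codes under the line "Subjects are excluded from PD analysis in case of these PDs". The codes are INCL01 (consent), INCL04 (class III or IV histology within 5 years) and INCL06 (UPCR of at least 0.5 mg/mg at screening and baseline).

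The primary UPCR estimand and the CRR estimand both sit in SAP section 6, titled "Statistical methods for Pharmacodynamic (PD) parameters". Protocol 8.5 likewise puts UPCR under a joint efficacy and pharmacodynamics heading. The estimand in SAP 6.1.1 gives a disease population, "Population: moderately active proliferative lupus nephritis patients", but no analysis set. The same section plans supportive work: "Additional analyses including all patients regardless of their adherence to treatment will be performed".

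**The concern.** The between-arm ratio and its confidence interval rest on the random allocation. Grouping by treatment received suits safety and PK, where exposure is the question. For efficacy it lets events after randomisation decide who is compared with whom. The placebo arm has about 20 patients (17 completers in the sample size calculation), so a single move carries weight.

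Three features of the text add to this:

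- The efficacy set is not named, so a programmer would have to infer it.
- Each patient has seven infusions, and neither document says which group a patient joins after receiving both CFZ533 and placebo.
- The estimand in SAP 6.1.1 deals with death, rescue medication and treatment discontinuation, and states that no other intercurrent event is considered. Receipt of the wrong treatment is therefore not covered there either.

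A secondary matter depends on the PD set being the one used. In that case randomised patients with INCL04 or INCL06 deviations drop out of the primary analysis.

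**Working it through.** **Inputs (Protocol 11.7).** One-sided alpha 10%; true ratio 0.64, so the log difference is ln 0.64 = -0.446; SD 0.7, taken as log scale; 34 + 17 completers; 60 enrolled as 40 + 20; point-estimate criterion of a ratio at or below 0.80 (log -0.223).

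**1. The plan's own figures.** SE = 0.7 × √(1/34 + 1/17) = 0.2079. The significance limit is 1.2816 × 0.2079 = 0.266, a ratio of about 0.77. This is stricter than 0.80, so it alone sets the power: Φ((0.446 - 0.266)/0.2079) = 80.6% (80.1% with the noncentral t). The stated power of about 80% reproduces, and so does 51/0.85 = 60. The sample size is not in question.

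**2. Leverage of one regrouped patient.** Let the placebo mean be 0, the CFZ533 mean be -0.446, and the moved placebo patient's value be x. The change in the log difference is

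(x + 0.446)/(n_CFZ + 1) + x/(n_pbo - 1).

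| Arms | x | Change in log difference | Factor on ratio |
|---|---|---|---|
| 40:20 | +0.7 | 1.146/41 + 0.7/19 = +0.065 | 1.07 |
| 40:20 | -0.7 | -0.254/41 - 0.7/19 = -0.043 | 0.96 |
| 34:17 | +0.7 | 1.146/35 + 0.7/16 = +0.077 | 1.08 |
| 34:17 | -0.7 | -0.254/35 - 0.7/16 = -0.051 | 0.95 |

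At 40:20 an estimate of 0.64 would become about 0.68 or 0.61. Both stay inside the success limits of about 0.77 (significance) and 0.80 (point estimate). One patient changes the decision only when the estimate is already near a limit.

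**3. Expected shift, as distinct from leverage.** Suppose a placebo-randomised patient did receive CFZ533 throughout, for reasons unrelated to outcome. Under the assumed effect that patient is centred on -0.446.

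- Grouped as treated, the expected shift is zero.
- Grouped as randomised, the placebo mean moves by 0.446/20 = 0.022, so the ratio is attenuated by about 2%, from 0.64 to about 0.65.
- With 17 placebo completers the attenuation is 0.446/17 = 0.026, and power falls from 80.6% to 77.0%.

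**4. Eligibility exclusions (assumed counts; the documents give none).** Dropping patients from the 51 completers at 2:1:

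| Dropped | Power |
|---|---|
| 0 | 80.6% |
| 2 | 79.5% |
| 3 | 78.8% |
| 5 | 77.5% |
| 6 | 76.9% |

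**5. Whether other text restores the randomised comparison.** The supportive analyses in SAP 6.1.1 bring back patients regardless of adherence. They say nothing about grouping, so the rule in SAP section 4 still governs them. The estimand's population line describes a disease, not a set or a grouping.

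**The case against.** The best defence is that the rule may never bite. Kits are assigned through the IRT system (Protocol 6.3), and nothing suggests a wrong kit was given. If none is, the two groupings coincide for treated patients. If errors occur but are unrelated to outcome, step 3 shows that as-treated grouping has no expected shift, while as-randomised grouping dilutes slightly. The study is also exploratory. All of this stands, and it limits the size of the point. It does not justify the rule: whether an error is unrelated to outcome cannot be checked from a handful of cases, and grouping by randomised arm does not need that assumption.

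A reader might infer three stronger things that the documents do not support.

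- *That the INCL04 and INCL06 exclusions break randomisation.* Both are judged on data from before randomisation, so treatment cannot affect them. Applied alike in both arms, they cost precision and narrow the population. Few cases should arise, because Protocol section 4 bars anyone with an eligibility deviation from randomisation.
- *That the primary analysis certainly uses the PD set.* This is a reasonable inference from where UPCR is placed, but no visible text says it. SAP 6.1.1 has blacked-out text between the estimand and the model, and Protocol 11.4.5 on sensitivity analyses is also blacked out.
- *That the same exclusions are wrong for the PK set.* Protocol 3.3.1 links class III and IV disease to raised renal CD40, and raised CD40 to faster elimination of CFZ533. It also cites an association between proteinuria and clearance for another antibody in SLE. It adds that renal clearance is usually minor for molecules of this size, so the link is arguable, but a rationale exists. PK set membership has no bearing on the efficacy comparison.

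**Conclusion.** The point holds in a limited form. As-treated grouping is explicit in both documents and applies to whichever set serves the primary UPCR analysis. No alternative grouped by randomised arm is defined. The consequence is conditional on at least one patient receiving the wrong treatment.

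The 4% to 7% movement at 40:20 (5% to 8% at 34:17) shows how much one patient can weigh, assuming SD 0.7, a true ratio of 0.64 and a patient 1 SD from the placebo mean. It should not be read as an expected bias.

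The eligibility exclusions are secondary and conditional on the PD set being used. Losing 3 of 51 completers, an assumed count, costs about 2 percentage points of power (80.6% to 78.8%).

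The change is worth making because it protects the randomised comparison at almost no cost.

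**What to change.** - Define a full analysis set: all randomised patients who received study drug and gave valid consent (keep the INCL01 exclusion), analysed by randomised arm.
- Name this set in SAP 6.1 and 6.2 for the UPCR and CRR analyses, and state that the supportive analyses regardless of adherence use the same grouping.
- Do not apply the INCL04 and INCL06 exclusions to it. If they are of interest, use them only in a supportive analysis.
- Keep as-treated grouping for safety and PK, and leave the PK-set exclusions as they are.
- Align the opening sentence of Protocol 11.1 with SAP section 4. Table 4-1 already requires any update by SAP amendment before database lock.

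The cost is amended wording and one extra population flag, with no new data. The statistical price is a slight dilution if a patient does receive the wrong treatment: about 2% on the ratio for each placebo patient fully treated with CFZ533, at 20 placebo patients and the assumed effect. The change leaves the estimand's handling of rescue medication and discontinuation as it is.

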11.2 Subject demographics and other baseline characteristics

All data for background and demographic variables will be listed by treatment group and subject. Summary statistics will be provided by treatment group.

Relevant medical history, current medical conditions, results of laboratory screens, drug tests and any other relevant information will be listed by treatment group and subject.

11.3 Treatments

Data for study drug administration (rescue medication) and concomitant therapies will be listed by treatment group and subject.

11.4 Analysis of the primary variable(s)

11.4.1 Primary Variable(s)

The primary variable is the ratio from baseline in first morning void urinary protein creatinine ratio (UPCR) at Week 25.

11.4.2 Statistical model, hypothesis, and method of analysis

The ratio from baseline in first morning void UPCR will be log transformed prior to the analysis. A repeated measures mixed model will be fitted with factors for treatment group (CFZ533 or placebo) and visit (e.g. Week 5, 9, 13 etc.). The model will also include a factor for the prednisone dose-equivalent at baseline (≤ 10 mg, > 10 mg), which is a stratification factor for the randomization. Log-transformed baseline first morning void UPCR will be included in the model as a covariate along with the interactions between visit and all of the fixed effects. A normal errors model will be assumed with an unstructured covariance matrix to account for the correlation within subjects. The model will be estimated using maximum likelihood techniques.

At each of the visits, the difference between the CFZ533 and placebo group will be estimated (along with its corresponding 95% confidence interval) and then back-transformed to provide an estimate of the ratio between treatment groups.

11.4.3 Handling of missing values/censoring/discontinuations

Data from patients taking rescue medication during the trial (or failing to tolerate steroid taper, for patients receiving oral corticosteroid at baseline) will be excluded from the date of rescue medication intake. Data from patients who discontinue study treatment will also be excluded, from the date of study drug discontinuation. The primary analysis is unbiased under the assumption that the missing data are missing at random (MAR).

If the UPCR from the first morning void sample is not available, then the UPCR from the corresponding spot sample taken at the investigator site will be used in the analyses.

11.4.4 Summary statistics of safety

Vital signs

All vital signs data will be listed by treatment group, subject, and visit/time and if ranges are available abnormalities (and relevant orthostatic changes) will be flagged. Summary statistics will be provided by treatment and visit/time.

ECG evaluations

All ECG data will be listed by treatment group, subject and visit/time, abnormalities will be flagged. Summary statistics will be provided by treatment and visit/time.

Clinical laboratory evaluations

All laboratory data will be listed by treatment group, subject, and visit/time and if normal ranges are available abnormalities will be flagged. Summary statistics will be provided by treatment and visit/time.

Adverse events

All information obtained on adverse events will be displayed by treatment group and subject.

The number and percentage of subjects with adverse events will be tabulated by body system and preferred term with a breakdown by treatment. A subject with multiple adverse events within a body system is only counted once towards the total of this body system.

For serious adverse events and adverse events of special interest (AESI), statistical analyses comparing the event rates in two treatment groups will be performed.

